Rationale: Evidence-based treatments for posttraumatic stress disorder (PTSD), such as Eye Movement Desensitization and Reprocessing (EMDR) and Imagination and Rescripting Therapy (ImRs), are highly effective treatments in the majority of the PTSD patients. PTSD is highly comorbid with personality disorders (PD), especially borderline personality disorder (BPD), and cluster C - avoidant, dependent, or obsessive-compulsive - personality disorders (CPD). It is not clear yet what treatment is most effective for those who suffer from both PTSD and PD. There is growing motivation in clinicians to offer PTSD treatments to PTSD with comorbid PD, because these treatments are highly effective, relatively short (weekly sessions, 3-6 months) and there is some evidence that with PTSD treatment, comorbid PD symptoms might resolve as well. PTSD treatments are less time-consuming than PD treatments and - at least in the short term - financially attractive. However, at least 30-44% PTSD patients do not sufficiently respond to these treatments. Moreover, a high number of PTSD patients are excluded from these therapies because of suicidality, self-destructive behaviour or other personality problems. Therefore, it might be more efficient to add a PD treatment at the same time. Evidence-based treatments for personality disorders (PD), such as dialectical behaviour treatment (DBT) for BPD, and schema-focused treatment (SFT) for CPD are well established. These treatments are more intensive (twice a week for at least one year) than PTSD treatments. There is some evidence that integrated PTSDPD treatment is twice as effective on reducing PTSD symptoms than PD treatment alone, but integrated PTSD-PD treatment is not yet directly compared to PTSD treatment alone. This study will address this knowledge gap, including secondary outcome measures on functioning, quality of life and cost-effectiveness.

The result of this study might be that one or the other treatment works better, depending on the personal profile of the patient. So far, some psychological factors have been found

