to be associated with worse outcome of PTSD treatment. These are cognitive (educational level, working memory emotion regulation), affective (anger, sleep problems, dissociation), and relational factors (therapeutic alliance, attachment, social support). In addition, neurobiological factors are found to be associated with PTSD treatment outcome, such as increased activity connectivity of the limbic network and decreased activity and connectivity of the cognitive control networks, and disturbed hormonal levels and epigenetic factors (5-HTTLPR, BDNF, cortisol/FKBP5-methylation, oxytocin/OXTR). Because these candidate predictors are found on a group level (in non-responders vs. responders), they cannot directly be used on an individual level. By using machine-learning techniques we might use these candidate predictors on an individual level to guide treatment choices and thereby personalise psychiatry.

We hypothesize that in patients with PTSD with BPD, integrated DBT-EMDR treatment results in a higher effect size and higher response rate than EMDR-only (A1); in patients with PTSD and CPD, integrated SFT- ImRs treatment results in a higher effect size and higher response rate than ImRs only (A2). Furthermore, we hypothesize that non-response to PTSD-treatment can be individually predicted by a machine-learning model with (B1) psychological factors (cognitive, affective, and relational) and (B2) neurobiological factors (neural factors, and hormonal/ epigenetic factors).

Objective: In the current project, we will firstly study effectiveness of PTSD-treatment compared to integrated PTSD-PD-treatment in treatment-seeking, adult patients with comorbid PTSD and PD in a wide range of severity (minimally 4 criteria of a personality disorder). Secondly, we will investigate psychological (cognitive, affective, and relational) and neurobiological candidate predictors of treatment outcome, and use them in a machine-learning paradigm to come to a clinically useful and individual prediction instrument of treatment outcome.

Study design: Two related randomized controlled trials (A1, A2) with prediction analyses (B1, B2).

Study population: With the assumptions of a small effect size (< 0.5) of PTSD treatment in patients with comorbid PTSD and PD and a double effect size of integrated PTSD-PD-

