2. OBJECTIVES

The primary objectives of this study are:

- A. To investigate if in adult patients with PTSD and comorbid PD it is more effective to provide integrated PTSD-PD treatment compared to PTSD treatment alone in terms of response rate in PTSD symptoms:
 - A1. In patients with PTSD with BPD, integrated DBT-EMDR treatment results in a higher effect size and higher response rate than EMDR-only.

A2. In patients with PTSD and CPD, integrated SFT- ImRs treatment results in a higher effect size and higher response rate than ImRs -only.

B. To investigate individually prediction by a machine-learning model of PTSD treatment outcome in adult patients with comorbid PTSD and personality disorders (profiling), in order to improve treatment indication leading to more precise (personalized) and efficient treatments, with candidate predictors:

B1. Psychological factors: cognitive (educational level/IQ, working memory, emotion regulation), affective (hyper-arousal: anger, sleep; hyper-arousal: dissociation), and relational factors (therapeutic alliance, attachment, social support).

B2. Neurobiological factors: Neural factors (smaller ACC and hippocampus volume, increased right amygdala and ventral ACC activity and de/increased dorsal ACC activity), and Hormonal/ epigenetic factors (5-HTTLPR, BDNF, cortisol/FKBP5-methylation, oxytocin/OXTR).

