7.1 Primary study parameters

For population description, the CAPS-5, M.I.N.I.-plus, SCID-5-PD, will be used in addition to the CTQ, LEC-5, DERS, ITQ, PAI-BOR, STAS, PSQI, DES-II, WAV, RSQ, CPI, BDI, AUDIT, WHODAS, EQ5D-5L, and Tic-P will be used (see Table 1). The subgroup of patients that underwent MRI will be compared to the rest of the group to test for pretreatment differences in PTSD severity and type/severity of PD.

The primary analysis in the RCTs will be improvement of PTSD symptoms at 3 time points. This primary analysis will include trauma symptom scores at T₀, T₂ and T₄ (CAPS-5, severity score) in a repeated measurements model, a linear mixed model for repeated measurements including at least time points, treatment group, the interaction between time point and treatment, sex, age and severity as fixed factors, baseline score as covariate and subject as random intercept factor. An cAR(1) structure will be used to model the residual covariance matrix. Responders will be defined as participants with a posttest score at least 1 SD below the pretest score (based on Jacobsen and Truax, 1991).

Secondary analyses will examine whether hormonal and epigenetic factors (5-HTTLPR, BDNF, cortisol/FKBP5-methylation, oxytocin/OXTR) mediate the treatment effects. Mediation analyses will include levels of the aforementioned variables on T₀ and T₂ to estimate the direct and indirect paths of casual treatment on the primary and secondary study parameters, through the proposed mediators.

For individual prediction analyses, machine learning techniques (in R: supervised and unsupervised techniques, e.g. the random forest model method) will be applied to separate treatment responders from non-responders based on clinical and neurobiological candidate predictors and in order to define the predictors

contributing most to classification accuracy, calculating sensitivity, specificity, and positive and negative likelihood ratios from the prediction model (Ball et al., 2014).

Candidate predictors that will be used are:

- Psychological factors: Cognitive factors (educational level/IQ, working memory, emotion regulation), Affective factors (hyperarousal: anger, sleep; hyperarousal: dissociation), and Relational factors (therapeutic alliance, attachment, social support);

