- Neurobiological factors: Neural factors (smaller ACC and hippocampus volume, increased right amygdala and ventral ACC activity and de/increased dorsal ACC activity), and Hormonal/ epigenetic factors (5-HTTLPR, BDNF, cortisol/FKBP5-methylation, oxytocin/OXTR).

Questions that will be answered with machine learning in this study are:

1. Does brain activity predict treatment outcome for PTSD and PD (all treatment conditions together; N = 80)
2. Does brain activity predict treatment outcome for PTSD (EMDR and ImRs; N = 40)
3. Does brain activity predict treatment outcome for integrated PD/PTSD treatment (EMDR + DBT and ImRs + SFT, N = 40)
4. Data from the MRI at T2 can be used to predict relapse after treatment for all treatments together (N = 80 if all patients return for a second MRI) or for trauma treatment and integrated treatment separately (N = 40 for both).

fMRI data will be analysed with Statistical Parametric Mapping (SPM) software or FMRIB Software Library (FSL) to map connectivity in the brain. Standard group comparisons will be used to analyse structural and task-related (face recognition) fMRI. First, ANOVA analyses will be performed with patients vs. controls for baseline comparison. Second, full factorial analyses will be conducted in patients-only, with time (baseline vs. end of treatment) and condition (type of treatment) as factors to analyse the effect of treatment on (task-related) brain structure, connectivity and activity. Independent component analysis (ICA; FSL MELODIC) and dual regression analyses will be used to study changes in functional connectivity of brain networks (with a focus on the salience

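### Prediction is meant to guide the choice between PTSD-only and integrated treatment, but no planned analysis tests whether a predictor's effect differs between the randomised arms

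*Combined protocol and SAP*

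**What the plan says.** Treatment choice is a stated purpose. The Summary (Rationale) expects that the result may be that "one or the other treatment works better, depending on the personal profile of the patient", and hopes to "use these candidate predictors on an individual level to guide treatment choices and thereby personalise psychiatry". Its paragraph on burden and benefit repeats the aim. Objective B in section 2 is individual prediction of outcome, "in order to improve treatment indication leading to more precise (personalized) and efficient treatments".

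Section 7.1 says that machine-learning techniques "will be applied to separate treatment responders from non-responders based on clinical and neurobiological candidate predictors". The candidate list that follows has psychological, neural and hormonal/epigenetic factors. Treatment arm is not on it. The numbered questions concern brain activity:

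- Question 1 is pooled: "all treatment conditions together; N = 80".
- Question 2 stays within the PTSD-only arms: "Does brain activity predict treatment outcome for PTSD (EMDR and ImRs; N = 40".
- Question 3 stays within the integrated arms: "Does brain activity predict treatment outcome for integrated PD/PTSD treatment (EMDR + DBT and ImRs + SFT, N = 40".
- Question 4 uses the T2 scan to predict relapse, pooled or with the same split.

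For psychological predictors, question 4 under A1 and under A2 in section 5.3 puts the integrated component in brackets. It therefore leaves open whether the arms are modelled together or apart. Section 7.1 does not settle this for psychological or hormonal predictors.

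**The concern.** A factor that predicts outcome equally well under both treatments tells a patient how they are likely to fare, but not which treatment to take. Choosing requires the difference in effect between arms at a given profile. Randomisation identifies that difference, and the plan does not use it for this purpose.

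The layout also invites an informal comparison: a factor that predicts in one treatment type and not in the other looks like a reason to choose. The protocol's own introduction (Part B) sets treatment types against each other in this way for dissociation, as a predictor of worse response to PTSD treatment but not to integrated treatment. Finding an association in one group and none in another is not a test of difference, and with 40 per group the two results will often disagree by chance. What is at stake is the treatment-choice claim of Objective B. The efficacy comparisons A1 and A2 are not affected.

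**Working it through.** **What the planned terms estimate**

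| Planned analysis | What it estimates |
|---|---|
| Mixed model, time by treatment (7.1) | Average treatment effect over time |
| fMRI factorial, time and condition (7.1) | Effect of treatment on the brain |
| ML question 1 | Prognosis, arms mixed |
| ML questions 2 and 3 | Prognosis within each type |
| Sensitivity, specificity, likelihood ratios | Accuracy for response, not for benefit |

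None of these is a predictor-by-arm contrast.

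**The plan's own figure.** The only sample-size calculation (4.4) is for the main effect. Using the standard repeated-measures formula with difference 10 (0.5 × SD 20), correlation 0.7, 5 follow-ups, 80% power and an assumed two-sided alpha of 0.05:

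n = (1.96 + 0.84)² × 2 × 400 × (1 + 4 × 0.7) / (5 × 100) = 7.85 × 2 × 400 × 3.8 / 500 ≈ 47.7.

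That gives 48 per condition against 50 stated, so it reproduces within two patients. The prediction sizes of 80 and 40 have no power or precision basis.

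**Inputs for the check.** MRI: 40 per treatment type (4.1, 7.1). All patients: 63 per arm, so 2 × 63 = 126 per type across the two RCTs, or about 94 after 25% drop-out (126 × 0.75 = 94.5). The correlations and the two-sided 0.05 level are assumptions.

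**A predictor with the same effect in both types.** Power within one type is p ≈ Φ(atanh(r)√(n−3) − 1.96). The chance of significance in exactly one type is 2p(1−p). For n = 40, √37 = 6.08:

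| r | p | 2p(1−p) |
|---|---|---|
| 0.2 | 0.23 | 0.36 |
| 0.3 | 0.47 | 0.50 |
| 0.4 | 0.73 | 0.39 |
| 0.5 | 0.92 | 0.15 |

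With 30 per type (25% loss) the last column becomes 0.30, 0.46, 0.48 and 0.30. A direct contrast has a false-positive rate of 0.05 per predictor.

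**Closer to a ranking.** I simulated 4,000 trials per setting with 40 per type, a 60/40 responder split (the Summary gives 30-44% non-response), independent predictors and no true interaction. The predictor counts, 5 neural and 18 in all, are taken from the list in 7.1.

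| | 5 predictors | 18 predictors |
|---|---|---|
| At least one predictor significant in one type only | 38-81% | 84-96% |
| Top-ranked predictor differs between types | 30-79% | 75-95% |
| At least one false interaction, unadjusted | 21-24% | 59-60% |

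The last row agrees with 1 − 0.95¹⁸ = 0.60. A direct contrast also needs multiplicity control.

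**Power of the direct contrast.** The standard error of a difference in Fisher z is √(2/(n−3)). For a difference of 0.4 (roughly r = 0.4 against 0):

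| n per group | SE | Power |
|---|---|---|
| 40 (MRI) | 0.233 | 41% |
| 47 (one RCT, after drop-out) | 0.213 | 47% |
| 63 (one RCT) | 0.183 | 59% |
| 94 (both RCTs, after drop-out) | 0.148 | 77% |
| 126 (both RCTs) | 0.128 | 88% |

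For r = 0.3 against 0, power is 27% at 40, 40% at 63, 55% at 94 and 68% at 126.

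**The case against.** Four points can fairly be made for the plan.

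- **It answers its formal hypothesis.** Hypothesis B is that non-response to each treatment type can be predicted, and questions 2 and 3 address that for brain activity. The introduction calls this work exploratory, and the sentence on profile-dependent benefit is worded as a possibility. This stands, and it limits the weight of the point. It does not remove the gap, because treatment indication is written into Objective B as its purpose.
- **The within-type models are usable.** A reader might infer that separate models can never inform treatment choice. That goes too far. Both types are randomised, so the difference between the two models' predictions for one patient is a legitimate estimate of benefit. What is missing is that contrast and its validation.
- **No false claim is planned.** A reader might also infer that false arm-specific predictors are bound to follow. The documents do not say that a predictor found in one type only will be read as specific to it. They neither plan nor exclude that comparison, so this is a substantial risk and not a certainty.
- **The scope is narrower than all prediction analyses.** The pooled and within-type list covers brain activity only. For other predictors the structure is unstated, which leaves the contrast unplanned there too.

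The significance criterion is also a stand-in: the plan has no p-value rule for single predictors. Disagreement of the top-ranked predictor is the closer guide, and it points the same way.

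**Conclusion.** The point holds as an omission. Guiding treatment choice is an aim, and no planned analysis tests whether a predictor's effect differs between PTSD-only and integrated treatment. As planned, the models support prognostic statements.

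The 36-50% at 40 per type assumes equal true correlations of 0.2-0.4 and a two-sided 0.05 criterion. It falls to 15% at 0.5. The 5% for the direct contrast is per predictor and applies to an unpenalised test.

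The 77-88% power with 94-126 per type requires the same interaction in both RCTs, which differ in personality disorder and in trauma treatment. Without that assumption it is about 59% within one RCT at 63 per arm. In the MRI subset it is about 41%, so only large differences could be detected there. This is a worthwhile and cheap improvement to the secondary part of the trial.

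**What to change.** Pre-specify one differential-prediction analysis in all randomised patients who have the predictor measured at T0, stratified by RCT (A1, A2). Either of two forms would serve:

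- a model of T4 CAPS-5 on baseline CAPS-5, arm, baseline predictors and penalised arm-by-predictor terms; or
- a cross-validated contrast of predicted benefit between arm-specific models.

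State how multiplicity is handled. Penalised estimates do not carry a 5% error rate by themselves, so name the joint test, adjustment or cross-validated criterion that will support a claim.

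Two limits follow from the schedule. Therapeutic alliance should stay out of the interaction terms, because Table 1 has no T0 mark for it and it would be a post-randomisation variable. Hormonal and genetic predictors should be used only in patients who gave samples, since Table 3 and the T2 visit text in section 5.3 suggest that these are a subgroup.

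State the model structure for psychological and hormonal predictors. Base treatment-choice statements only on the contrast. Label pooled and within-type models, including all MRI models, as prognostic and exploratory, and state the low power in the MRI subset. The N = 80 for question 4 should also be reconciled with section 4.4, which expects about 40 second scans, or some 20 per type if evenly split.

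The cost is analysis time on data already being collected. The downside is lower precision and fewer claims.

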4. STUDY POPULATION

4.1 Population

The study population consists of all patients between 18-65 years old, referred to the SC with comorbid PTSD and PD, who are willing to participate in the study (informed consent); N = 252 patients (see 4.4), of which sub-group of 80 patients (N = 40 Condition 1 + 40 Condition 2) will participate in the MRI study (before and after treatment). For baseline MRI comparison, extra 40 healthy controls, matched on age, gender and educational level, will be recruited also for the MRI study via advertisements in local newspapers and through hersenonderzoek.nl. In total, 292 persons will be included in this study.

A pilot episode will be introduced (September – December 2017) to test the feasibility of the study and inclusion rate. Feasibility is enhanced by the opportunity to build on the established expertise of the academic research group in Arkin – Research and VUmc in conducting effect studies, longitudinal and neurobiological studies.

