4.4 Sample size calculation

A power calculation was made based on Twisk (2007). We assume that PTSD treatment (EMDR or ImRs) have a small effect size (< 0.5) in the complex patient group with PTSD and comorbid

CPD/BPD, while the integrated treatment will show double effect sizes (1.0) (Harned et al., 2014). With a minimal clinical relevant difference of a 0.5SD on the CAPS-5, and the assumptions of a SD of 20.0, an intra-person correlation coefficient of 0.7, 5 follow-up measurements, the needed number to include is 50 persons per condition to reach for 80% power. Expecting a drop-out rate of 25%, we will include 63 persons per arm, or for 4 arms in total 252 persons.

In 2016, approximately 950 new patients were referred to the SC (Amstelveen). From these patients, ca. 450 had PTSD. From these PTSD patients, 168 had a comorbid PD and 188 more were not assessed for personality traits (“Uitgestelde diagnose”). We expect that introducing the assessment of axis II assessments with this study will result in an estimated 300 patients with PTSD and PD per year, and after 33% refusals or exclusions, in an estimated 200 patients possible to include per year. To be sure to include enough patients, we will need to include more patients from another site of the

Sinai Center, i.e. Amersfoort (400 patients, from which 216 PTSD patients, from which an estimated 100 PTSD + PD patients), and extend the inclusion period.

From these 252 patients, 80 will be asked for additional MRI, next to 40 healthy controls (Total sample size = 292). An estimated 40 patients will be available for a second MRI after 6 months (total of 160 scan sessions).

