Blood samples will be collected in 3 x 6ml tubes and the frozen samples will be stored at -80°C for intended future assaying of inflammatory markers (see Coelho et al., 2014), neuropeptides (such as oxytocin, 5HT), and epigenetics (such as FKBP5-methylation, OXTR- & 5HTTLPRgenes). The tubes will be stored without personal data linked to it, and they will only be marked with a subject number as described in section 9.1. below. Cortisol level (HPA-indicator) will be assessed in hair. This sample can be collected non-invasively by cutting a 1-cm distal to the scalp (1 month's exposure) sample of hair (Russell et al., 2012). All samples will be stored for 15 years (according to Archiefwet 1995).

In a subgroup: MRI session

Exclusion criteria for MRI research will be checked (metal implants, pregnancy, somatic disorders interfering with brain functioning, other (psycho-)pharmaca than at-least-3-months stabile dose SSRI or low-dose benzodiazepines, claustrophobia). A separate visit for MR scanning will be planned within 2 weeks of To, before the start of treatment, without causing a delay in treatment start. MRI sessions take at maximum 60 minutes (30-min functional MRI with a face recognition, and a suppression vs. reappraisal task, 5-min structural MRI, 8-min resting state MRI; and 8-min DTI) plus 30 min preparation. Next to patients, 40 healthy control persons, matched for age, gender, and education, will be asked to participate in one MRI session (no repeat MRI). These healthy control persons will be recruited via advertisements in local papers.

T1, T3 and FU

Patients do not have to come to the study center for T1, T3 and FU and can fill in the questionnaires via a login code at home if they have access to the internet (see Table 1.). Child trauma and life events questionnaires are only done at baseline (CTQ, LEC-5). Total duration of these measurements (T1, T3 and FU) will be between 15 and 30 minutes (see Table 3).

T2 visit

From all participants whose blood and hair was collected at baseline, blood and hair will be collected at T2 as well (duration 30 minutes). All participants who participated in the fMRI study at baseline will have their second MRI at T2. (duration 90 minutes). At T2, the CAPS-5 will also be conducted and participants will fill out the same questionnaires as at T0, except for the CTQ and LEC-5. Total duration of these measurements of will be ca. 2 hours (see Table 3).

Extra contact moment

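### The MRI controls are matched to patients on age, gender and educational level, but the baseline comparison in 7.1 names no adjustment for these factors; adding them is almost free and may gain precision

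*Combined protocol and SAP*

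**What the plan says.** Section 4.1 sets up the control group for a baseline MRI comparison: "extra 40 healthy controls, matched on age, gender and educational level, will be recruited also for the MRI study". Section 5.3 repeats the matching and limits controls to one scan: "40 healthy control persons, matched for age, gender, and education, will be asked to participate in one MRI session". Section 4.4 gives the planned sizes as 80 patients and 40 controls. None of these sections says whether matching is by pair, by set of one control and two patients, or by group frequencies.

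Section 7.1 introduces the imaging analysis with "Standard group comparisons will be used to analyse structural and task-related (face recognition) fMRI" and then gives the one test that involves controls: "First, ANOVA analyses will be performed with patients vs. controls for baseline comparison". No covariate, pair or set term is named. The imaging analyses that follow are restricted to patients or compare treatment conditions and time points, so this is the only named analysis that uses the control group.

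Earlier in the same section, the CAPS-5 mixed model does have its covariates spelled out: "the interaction between time point and treatment, sex, age and severity as fixed factors, baseline score as covariate and subject as random intercept factor".

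**The concern.** Matching makes the two groups alike on the matching factors, so the difference in group means varies less from sample to sample than it would with independently drawn groups. An ANOVA with group as its only factor does not use this. Variation due to age, gender and educational level stays in the error term, and the standard error describes a noisier comparison than the one carried out. The result is intervals wider than necessary and a test that rejects less often than its nominal level.

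That reasoning needs close balance. With 40 controls recruited by advertisement, twice as many patients and no stated matching method, balance may not be close. The problem is then a different one: an unadjusted difference partly reflects whatever imbalance remains. Both problems have the same remedy, but they arise under opposite conditions and should not be claimed together.

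At stake is the precision of the baseline patient–control contrast, and how well it is protected against residual imbalance.

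**Working it through.** **Figures in the plan.** The documents give no effect size, SD, significance level or power for this contrast, so there is no figure to reproduce. The calculation in section 4.4 concerns the CAPS-5 only. The counts agree with each other: 252 + 40 = 292 participants, and 80 + 40 + 40 = 160 scan sessions, which fits one scan per control.

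**Inputs.** From the plan: 80 patients, 40 controls, three matching factors, no adjustment named. Assumed: a single outcome with total SD 1, a true difference of 0.5 SD, a two-sided 5% test, close balance, and R² from 0 to 0.5.

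**Standard errors.** The unadjusted standard error is √(1/40 + 1/80) = √0.0375 = 0.194. Under close balance the true variance of the difference is (1 − R²)(1/40 + 1/80). The unadjusted standard error is therefore too large by 1/√(1 − R²).

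**Type I error and power.** Write t = √(1 − R²).
- Actual type I error of the unadjusted test: 2[1 − Φ(1.96/t)].
- Power, unadjusted: Φ[(0.5/0.194 − 1.96)/t].
- Power, adjusted: Φ[0.5/(0.194 t) − 1.96].

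At R² = 0, 0.5/0.194 = 2.58 and Φ(2.58 − 1.96) = Φ(0.62) = 73%. At R² = 0.3, t = 0.837, so unadjusted power is Φ(0.62/0.837) = 77% and adjusted power is Φ(2.58/0.837 − 1.96) = 87%.

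| R² (assumed) | SE too wide by | Actual type I error, unadjusted | Power, unadjusted | Power, adjusted |
|---|---|---|---|---|
| 0 | 1.00 | 5.0% | 73% | 73% |
| 0.1 | 1.05 | 3.9% | 74% | 78% |
| 0.2 | 1.12 | 2.8% | 76% | 82% |
| 0.3 | 1.20 | 1.9% | 77% | 87% |
| 0.5 | 1.41 | 0.6% | 81% | 96% |

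**Check by simulation.** In 20,000 simulated studies of 40 sets (one control and two patients sharing a matching score), at R² = 0.3, type I error was 2.1% unadjusted, 5.0% with the score as covariate and 5.0% with a matched-set term. Power was 75.6%, 85.8% and 85.6%. At R² = 0, power was 72.9%, 72.9% and 72.2%. Covariate adjustment therefore recovers what a set analysis would, and it does not require sets to exist.

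**If balance is imperfect.** Suppose the groups differ by δ SD on a score that explains R² of the outcome. The unadjusted difference is then biased by √R² × δ outcome SDs: 0.32 δ at R² = 0.1 and 0.55 δ at R² = 0.3. The plan gives no basis for a value of δ.

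**The case against.** Five points can be made for the plan as written.

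1. *The plan is silent on covariates; it does not exclude them.* The sentence names a contrast, and an ANOVA in an imaging package can carry covariates. This stands as far as it goes: the supportable statement is that adjustment is not specified. But the same section lists covariates for the CAPS-5 model, so a reader would take the imaging model to have none.

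2. *The matching is not wasted.* A reader might infer that an unadjusted analysis throws away the benefit of matching. It does not. Matching still limits confounding without adjustment. In the table, unadjusted power also rises from 73% to 81% as R² increases, because the difference itself is less variable. What is missed is a further gain.

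3. *The size rests on assumptions.* This stands. R², the 0.5 SD difference and the single 5% test are all assumed, and nothing in the documents supports the upper end of the R² range. The planned analyses cover brain maps, so power for one scalar outcome does not carry over directly.

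4. *Under close balance the error is conservative.* This stands. A reader might infer that false positives are inflated; under close balance the opposite is true.

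5. *The contrast is peripheral.* This stands too. The objectives in section 2 and the project questions in section 5.3 concern treatment effect, mechanism and prediction in patients. None asks how patients differ from healthy controls.

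**Conclusion.** The point holds in a conditional form. The controls are matched on three factors, and the only named comparison that uses them has no term for those factors. To the extent that the factors predict a given MRI outcome and balance is close, the standard error is too wide and the test conservative. At an assumed 0.5 SD difference the forgone power is nil at R² = 0, about 3 points at 0.1 (74.4% against 77.7%) and about 10 points at 0.3 (77.1% against 87.0%). If balance is not close, the concern is residual confounding, of unknown size.

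A reader might go further and conclude that power is certainly lost, or that the trial's main result is weakened. The documents support neither. They give no figure linking the matching factors to any MRI outcome. The randomised CAPS-5 comparison and the prediction models do not use the controls. Nor do they specify a resting-state comparison with controls, so the point covers the structural and task-related data only. This is a low-priority improvement.

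**What to change.** In section 7.1, replace the sentence on the baseline ANOVA with wording such as:

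> The baseline patient–control comparison of structural and task-related MRI will use a general linear model (ANCOVA) with group as factor and age, gender and educational level as covariates.

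Add that any other comparison with controls actually carried out will use the same covariates. It would also help to state in section 4.1 whether matching is by pair, by set or by frequency, although the covariate model works under each.

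The cost is small. The unadjusted model has 120 − 2 = 118 error degrees of freedom. Three single-degree covariates leave 115, or slightly fewer if educational level enters as several categories. The values are already needed to do the matching, and Table 1 has the controls completing the demographic questionnaire. No new data or participants are required. Fixing the covariates before the scans are analysed also removes a choice that could otherwise be made after seeing results.
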